## 7 DATA COLLECTION

**WP1.** The National Neonatal Research Database contains quality-assured data (the Neonatal Data Set, an NHS Information Standard; DAPB1595). Information security management at the University of Edinburgh (Edinburgh Parallel Computer Centre, EPCC) is externally accredited as ISO 27001 compliant (Certificate number #276767-2018-AIS-GBR-UKAS). Records of infants will be linked to the National Pupil Database (NPD) in an NHS Trusted Research Environment (e.g. iCARE, the Imperial NHS Trust TRE) and ScotXed/SQA Pupil-Census in Scotland using date of birth, postcode and sex. De-identified datasets will be analysed using secure UoE or Imperial computers by members of the research team.

The NNRD contains data from  $>100,000$  infants in the required gestational range and 2-year outcome data are available for  $>60\%$  ( $>70\%$  in most recent years). Record linkage and data analysis will be carried out within the research team.

**WP2 and 3.** Contact data and research data will be stored separately, linked by a unique participant identifier. Electronic data will be collected and managed using REDCap (a secure, web-based application) and stored on a University of Edinburgh server that is hosted and managed by the Edinburgh Clinical Trials Unit. This protocol is in line with the University's Data Policy and the Data Protection Act of 1998. Data will be entered to a REDCap database with an SOP to govern data completeness, accuracy and validity.

**Neuroimaging.** Full details of the neonatal imaging protocol are given in a published open-access paper and the 5-year protocol has been developed through a completed pilot study. All MRI is acquired using a brain optimised research scanner within a tight quality-controlled environment at Edinburgh Imaging. Neuroimaging data will be collected by brain research radiographers and subject to Edinburgh Imaging QC procedures. Structural MRI data are reported according to a structured report by a paediatric radiologist, including for incidental findings.

**HPA axis activity.** We will collect the following samples: i) endogenous glucocorticoids and metabolites (*glucocorticoid release*) in umbilical cord blood; ii) glucocorticoid receptor in cord blood leukocytes (*glucocorticoid signalling*); iii) maternal and infant hair cortisol at birth and infant hair cortisol at term

equivalent age (*overall glucocorticoid secretion*). Sample collection will conform to an SOP, and analysis will use published, validated methods for measuring metabolites from hair and blood at the UoE Clinical Research Facility Mass Spectrometry Core . The 5-year saliva cortisol samples (on waking, 30 minutes after waking and bed-time) are being collected as part of the TEBC protocol.

**DNAm.** Saliva DNAm will be sampled from preterm infants at term equivalent age to reflect the allostatic load of perinatal inflammation. Saliva will be collected in Oragene OG-575 Assisted Collection kits, by DNA Genotek, and according to an SOP. DNAm analysis using the Illumina Human MethylationEPIC BeadChip is established in the Edinburgh Clinical Research Facility Genetics Core.

**Questionnaire and records.** Demographic and clinical information will be extracted from the maternal and infant record by a member of the research team. The tools to assess cognition, behaviour, well-being and family circumstances are listed in Tables 1 and 2. Hard copies will be stored securely in locked filing cabinets in a locked room to which only study researchers have access.

The programme manager will oversee data collection, ensuring that time-points are adhered to for each participant. Participants will be contacted by post and / or telephone to arrange appointments and to prompt if questionnaires have not been returned, to maximise completeness of data collection.

## 7.1 Source Data Documentation

**WP1**, source data are: NNRD, the National Pupil Database, and the ScotXeD Pupil Census. Record-linkage will take place in an NHS Trusted Research Environment

**WP2** and **WP3**, source data are: NHS Lothian maternity and infant TRAK, Infant Badgernet, questionnaires. Some source data will be captured in the Case Report Form. Source data is defined as all information in original records and certified copies of original records or clinical findings, observations, or other activities in a clinical study necessary for the reconstruction and evaluation of the study. Source data are contained in source documents.

## 7.2 Case Report Forms

Paper case report forms will be used to collect demographic, SES, and medical information from records and questionnaires. Data will be transcribed to REDCap with an SOP to govern data completeness, accuracy and validity.

# 8 DATA MANAGEMENT

## 8.1 Personal Data

**WP1:** The National Neonatal Research Database contains quality-assured data (the Neonatal Data Set, an NHS Information Standard; SCCI1595). Records of infants will be linked using date of birth, postcode and sex. De-identified datasets will be stored and analysed on a secure university system.

**WP2:** Personal data will include name, CHI number of mother and infant, address, email, telephone number, date of birth of infant, ethnicity and health data. Participants will be issued with a unique identifier at the point of recruitment and this shall be used to label all research data including biological samples. Contact data and research data will be stored separately, linked by the unique identifier.

**WP3:** Personal data will include name, CHI number of mother and infant, address, email, telephone number, date of birth of infant, ethnicity and health data. Participants will be issued with a unique identifier at the point of recruitment and this shall be used to label all research data including biological samples. Contact data and research data will be stored separately, linked by the unique identifier.

## 8.2 Data Information Flow

**WP1:** Records from the National Neonatal Research database will be linked to the National Pupil Database (NPD) in an NHS Trusted Research Environment (e.g. SAIL Databank) and ScotXeD/SQA Pupil-Census in Scotland.

**WP2:** All research data will be collected by a member of the research team. The study coordinator will oversee data collection, ensuring that time-points are adhered to for each participant. Participants will be contacted by post and/or telephone to arrange appointments and to prompt if questionnaires have not been returned, to maximise completeness of data collection. No personal data will flow after assignment of the unique identifier.

The MRI community has developed methods for anonymizing MRI data – namely, ensuring that identifying information (e.g., birth date, sex) is unattached from shared data, and “de-facing” the data. There are several algorithms for defacing MRI data (e.g., FreeSurfer’s `mri_deface`). We will employ best practices for deidentifying and anonymizing MRI data prior to sharing. We will also ensure that participants understand the way that their data will be shared and obtain their consent. The risk of identification from MRI is low.

**WP3:** All research data will be collected by a member of the research team. The study coordinator will oversee data collection, ensuring that time-points are adhered to for each participant. Participants will be contacted by post and/or telephone to arrange appointments and to prompt if questionnaires have not been returned, to maximise completeness of data collection. No personal data will flow after assignment of the unique identifier, with the exception of tasks that are video recorded (Theory of Mind booklet, parent-child play, novel toy task, EF tasks). The data will be stored securely on a password protected file on the University of Edinburgh DataStore facility, accessible only by members of the research team.

The MRI community has developed methods for anonymizing MRI data – namely, ensuring that identifying information (e.g., birth date, sex) is unattached from shared data, and “de-facing” the data. There are several algorithms for defacing MRI data (e.g., FreeSurfer’s `mri_deface`). We will employ best practices for deidentifying and anonymizing MRI data prior to sharing. We will also ensure that participants understand the way that their data will be shared and obtain their consent. The risk of identification from MRI is low.

## 8.3 Data Storage

**WP1:** The National Neonatal Research Database contains quality-assured data (the Neonatal Data Set, an NHS Information Standard; DAB1595).

**WP2:** Electronic data (including personal data) will be collected and managed using REDCap (a secure, web-based application) and stored on a University of Edinburgh server. This is in line with the University’s Data Policy and the Data Protection Act of 1998.

Neuroimaging data will be stored on a dedicated GPGPU server, accessible to members of the research team. HPA axis and DNAm data will be stored on UoE Research Data Management servers, supported by Information Services. The data in the RDM file-store is automatically replicated to an off-site disaster facility and is backed up with a 60-day retention period, with 10 days of file history online.

Hard copies will be stored securely in locked filing cabinets in a locked room within University of Edinburgh premises (MRC Centre for Reproductive Health) to which only study researchers have access.

**WP3:** Electronic data (including personal data) will be collected and managed using REDCap (a secure, web-based application) and stored on a University of Edinburgh server. For all tasks that are video recorded, we will generate spreadsheets (using participant IDs) that hold coded data, that are then also

entered into REDCap (a secure, HIPAA-compliant web-based application) and stored on the University of Edinburgh DataStore server. Information security management at the University of Edinburgh (Edinburgh Parallel Computer Centre, EPCC) is externally accredited as ISO 27001 compliant (Certificate number #276767-2018-AIS-GBR-UKAS). Electronic data will be collected and managed using REDCap. This is in line with the University's Data Policy and the Data Protection Act of 1998.

Neuroimaging data will be stored on a dedicated GPGPU server, accessible to members of the research team.

Hard copies will be stored securely in locked filing cabinets in a locked room within University of Edinburgh premises (MRC Centre for Reproductive Health) to which only study researchers have access.

## 8.4 Data Retention

The data generated by this programme will be available for use by the research and policy communities in perpetuity.

**WP2: (i) Neuroimaging.** Raw human neuroimaging data acquired in Edinburgh are archived indefinitely in safe, long term storage in Edinburgh Compute and Data Facility (ECDF). The image processing server is linked by automatic daily back-up to the off-site ECDF. The compute component of ECDF, Eddie, has built-in redundancy with error check and "self-healing," and is itself backed-up using 2 tape systems. **(ii) HPA axis.** Data will be stored securely under password protection using UoE DataShare, which is backed-up and maintained through UoE IT systems. **(iii) DNAm.** Raw .IDAT files will be stored on GEO indefinitely.

We have costed for University of Edinburgh storage with guaranteed backup and resilience for all new data generated. In the long-term, the University of Edinburgh provides a DataVault data retention service to archive golden copy research data, which is also appropriate for sensitive data types; no charges apply to  $\leq 100\text{GB}$ , which the phenotypic dataset will not exceed. A golden/master copy of new data will be migrated onto this service as part of the process of data curation at the end of the project. Pseudo anonymised data will be stored in DataVault for 10 years, at the end of that period the data will be anonymised.

**WP3: Neuroimaging.** Raw human neuroimaging data acquired in Edinburgh are archived indefinitely. The image processing server is linked by automatic daily back-up to the off-site Edinburgh Compute and Data Facility (ECDF). The compute component of ECDF, Eddie, has built-in redundancy with error check and "self-healing," and is itself backed-up using 2 tape systems.

We have costed for University of Edinburgh storage with guaranteed backup and resilience for all new data generated. In the long-term, the University of Edinburgh provides a DataVault data retention service to archive golden copy research data, which is also appropriate for sensitive data types; no charges apply to  $\leq 100\text{GB}$ , which the phenotypic dataset will not exceed. A golden/master copy of new data will be migrated onto this service as part of the process of data curation at the end of the project.

## 8.5 Disposal of Data

No data will be disposed.

## 8.6 External Transfer of Data

**WP1.** Not applicable

**WP2.** Data collected or generated by the study (including personal data) will not be transferred to any external individuals or organisations outside of the Sponsoring organisation(s), without completion of a data access agreement between Edinburgh University and a recipient scientist in a receiving institution. Requests for access to de-identified, anonymized data will be governed by the PRENCOG Data Access and Collaboration Policy, according to the following principles:

**Suitability for sharing.** The data proposed for collection is suitable for sharing and will be useful to cognitive and clinical neuroscientists, image scientists, and neurobiologists. It provides a rich characterization of brain function and structure in early childhood with novel contextual information – enabling these data to address a wide variety of questions beyond those described in this proposal.

**Discovery by potential users of the research data. (i) Neuroimaging** will be retained within the University of Edinburgh and software will be shared via a web portal with GitHub integration. **(ii) HPA axis.** De-identified data will be made available in publications and through repositories such as Edinburgh DataShare and FigShare. **(iii) DNAm.** DNAm will be placed on Gene Expression Omnibus (GEO). A website will be developed to describe the project, link to related activity, of Pi and Co-Is, and signpost outputs. We will publish a description of the project to include design, governance and data access arrangements. We will use social media to promote the resource.

**Governance of access.** The study management group will review data requests from potential users, who are required to complete data access agreements. Once requests are approved a Data Access Agreement is signed, supported by the UoE Research Office and the corresponding office of the recipient's institution.

**The study team's exclusive use of the data.** Acquisition of data will continue until the end of the project. Primary publications may take 9-12 months after the end of the project. Once published, data will be shared immediately. Unpublished data will be shared after 3 years.

**Restrictions or delays to sharing, with planned actions to limit such restrictions.** Participants will be asked to consent to anonymous data-sharing. Since all MRI, HPA axis data and DNAm data are anonymised at source, there should be not be issues relating to identifiability. There will be some delay while we publish primary results, although as described above this will be completed as soon as possible.

**Regulation of responsibilities of users.** External users will be bound by data access agreements developed by the study management group. The data access agreement will specify the user's responsibilities concerning the received data and will confirm that the data will not be used for purposes other than those detailed in the data access agreement.

**WP3.** Data collected or generated by the study (including personal data) will not be transferred to any external individuals or organisations outside of the Sponsoring organisation(s), without completion of a data access agreement between Edinburgh University and a recipient scientist in a receiving institution. Requests for access to de-identified, anonymized data will be governed by the PRENCOG Data Access and Collaboration Policy, according to the following principles:

**Suitability for sharing.** The data proposed for collection is suitable for sharing and will be useful to cognitive and clinical neuroscientists, image scientists, and neurobiologists. It provides a rich characterization of brain function and structure in early childhood with novel contextual information – enabling these data to address a wide variety of questions beyond those described in this proposal.

**Discovery by potential users of the research data. Neuroimaging** will be made available in a suitable image bank and software will be shared via a web portal with GitHub integration. A website will be developed to describe the project, link to related activity, of Pi and Co-Is, and signpost outputs. We will publish a description of the project to include design, governance and data access arrangements. We will use social media to promote the resource.

**Governance of access.** The study management group will review data requests from potential users, who are required to complete data access agreements. Once requests are approved a Data Access Agreement is signed, supported by the UoE Research Office and the corresponding office of the recipient's institution.

**The study team's exclusive use of the data.** Acquisition of data will continue until the end of the project. Primary publications may take 9-12 months after the end of the project. Once published, data will be shared immediately. Unpublished data will be shared after 3 years.

**Restrictions or delays to sharing, with planned actions to limit such restrictions.** Participants will be asked to consent to anonymous data-sharing. Since all MRI data are anonymised at source, there

should be not be issues relating to identifiability. There will be some delay while we publish primary results, although as described above this will be completed as soon as possible.

**Regulation of responsibilities of users.** External users will be bound by data access agreements developed by the study management group. The data access agreement will specify the user's responsibilities concerning the received data and will confirm that the data will not be used for purposes other than those detailed in the data access agreement.

## 8.7 Data Controller

The University of Edinburgh and NHS Lothian are joint data controllers along with any other entities involved in delivering the study that may be a data controller in accordance with applicable laws (e.g. the site).

## 8.8 Data Breaches

Any data breaches will be reported to the University of Edinburgh ([[contact]](mailto:[contact])) and NHS Lothian ([[contact]](mailto:[contact])) Data Protection Officers who will onward report to the relevant authority according to the appropriate timelines if required.

# 9 STATISTICS AND DATA ANALYSIS

## 9.1 SAMPLE SIZE CALCULATION

**WP1.** The NNRD contains data from >100,000 infants in the required gestational range and 2-year outcome data are available for >60% (>70% in most recent years). Data completeness is high for key perinatal variables e.g., 90% for postcode at time of birth (used to derive deprivation index) and 93% for maternal age, and is lower for others e.g., maternal ethnicity 78%. We will investigate whether there are systematic patterns in missingness and we will analyse whether data imputation improves prediction models (univariate imputations using the mean/median values, and joint variable information-theoretic probabilistic methods for joint [conditional] distributions of variables).

Sensitivity analyses will be used to assess the impact of missing outcome data. In addition to applying statistical hypothesis testing (to assess p-values and statistical significance), we will also explore different statistical machine learning methods, including robust training and model validation using standard approaches (e.g. K-fold cross validation).

**WP2.** Sample size for groupwise comparisons of image data using biological variables is based on properties of the chosen EoP image phenotypes, and term and preterm differences we have observed in predictor variables (i) hair cortisol concentrations: 401pg/mg(262-615) versus 82pg/mg(55-169), respectively; and (ii) group differences in DNAm CRP scores.

**WP3.** There are no prior fMRI studies of young children born preterm (2-6 years) from which to estimate the size of the effect of preterm birth on aspects of their functional brain responses. Given this, we performed an indicative power analysis to determine the sensitivity to detect individual differences in two measures of social brain development in 3- to 5-year-olds (n=65). In this sample, the effect size of age on inter-region correlations among social brain regions, controlling for participant motion, was  $r_s(62)=.48$ ,  $p=7.1 \times 10^{-5}$ , and the effect size of age on the functional maturity of this cortical network, controlling for motion, was  $r_s(62)=.40$ ,  $p=.001$ . These are medium-large effects. Sensitivity analyses with n=246 children and 90% power could detect effects larger than  $r=.20$ . The sample will enable subset analyses based on PTB-RFs identified in WP1. An indicative power estimate for subset analyses based on effect size of age between 3 and 5 years and assuming  $\alpha = .05$  and 90% power, is that fMRI data from n=42 or n=60 children, respectively, would detect the two effects above.

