## 4.2 INCLUSION CRITERIA

**WP1:** All neonates with GA < 32 weeks born in Great Britain and admitted to a neonatal unit. Data are available from England and Wales from 2012, and from Scotland from 2014.

**WP2:** Exposed: 300 preterm infants born at <32 weeks of gestational age (GA). Non-exposed comparators: 100 term infants born at >37 weeks of GA\*.

Preterm infants are included if a mother booked her pregnancy and delivered at Simpson Centre for Reproductive Health (SCRH, the study centre), or if a mother booked her pregnancy at a hospital outside the study centre but was transferred to it with her baby *in utero* due to planned or expected birth <32 weeks. Preterm infants who are transferred to SCRH *ex utero* for intensive care are not included.

\*GA is estimated based on first trimester ultrasound.

**WP3:** 300 participants (200 preterm infants and 100 comparators) in Theirworld Edinburgh Birth Cohort will be invited for MRI and cognitive assessments at age 5 years.

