Diffusion images will be pre-processed (realigned, co-registered to the anatomical, and normalised) to reduce distortion, and submitted to eddy-current and motion correction analyses using QSIprep. Diffusion data will be analysed with a tensor model. Tensor model metrics (fractional anisotropy [FA] and mean diffusivity [MD]) are well studied and can be interpreted within a large literature on white matter development. Specific tracts will be identified based on previous work on white matter development and particular cognitive functions (for example, for social cognition, we will focus on the arcuate fasciculus, inferior fronto-occipital fasciculus, and corpus callosum). Average FA and MD will be calculated within tracts that connect individually-defined functional ROIs (as defined above), per network. Additionally, metrics with increased biological specificity from more advanced biophysical models of the diffusion signal will be explored. For example, the NODDI model enables calculating the intracellular volume fraction of water (ICVF) and orientation dispersion index (ODI).

Structural images will be used as anatomical reference for the diffusion and fMRI data. Structural images will be processed using FreeSurfer performing cortical reconstruction and volumetric segmentation. This step will be run inside the QSIprep and fMRIPrep processes.

Linear and mixed effects regressions will be used. Analyses with neuroimaging measures will include participant motion and age as covariates. When multiple statistical tests within a family are conducted, Bonferroni corrections will be applied.

In neuroimaging analyses, we will control type 1 error while minimising the risk of type 2 error by use of family-wise error rate and threshold-free cluster enhancement.

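### The WP3 power figures hold for one test at unadjusted alpha .05, but the plan applies Bonferroni within families, and n=42/60 rests on a benchmark age effect, not a PTB-RF effect

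*Protocol*

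**What the plan says.** Section 9.1 (WP3) explains why a proxy is used: "There are no prior fMRI studies of young children born preterm (2-6 years) from which to estimate the size of the effect". It takes two correlations with age from a sample of 65 children aged 3 to 5: .48 for inter-region correlations among social brain regions and .40 for functional maturity of that network, both controlling for motion. Two power statements follow.

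- Full sample, with the threshold put at r=.20: "Sensitivity analyses with n=246 children and 90% power could detect effects larger than" that value. No alpha is given in that sentence.
- Subsets defined by the risk factors from WP1. The basis is described as "An indicative power estimate for subset analyses based on effect size of age between 3 and 5 years". Alpha is set at .05 with power of 90%, and the stated result is: "fMRI data from n=42 or n=60 children, respectively, would detect the two effects above".

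Section 9.2 (WP3) defines functional maturity and inter-region correlation for social, attention and language networks. It then says: "When multiple statistical tests within a family are conducted, Bonferroni corrections will be applied". On covariates: "Analyses with neuroimaging measures will include participant motion and age as covariates". Section 4.2 says the 300 participants "in Theirworld Edinburgh Birth Cohort will be invited for MRI and cognitive assessments at age 5 years".

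**The concern.** Two assumptions behind the power figures do not match the analysis they support.

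The first is alpha. The subset figures are stated at .05 with no allowance for multiplicity, and the full-sample figure fits the same level. The analysis section commits WP3 to a stricter threshold whenever a family holds several tests, and at least two measures are planned.

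The second is the effect. The subset analyses concern PTB-RFs; hypothesis 3iii says these predict structural and functional maturity at 5 years. The subset sizes come instead from the correlation with age over a two-year span of development. In WP3 everyone is assessed at 5 years, and age is an adjustment variable.

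At stake is how the results are read. The n=42/60 sentence is the only numerical support for the statement that the sample allows PTB-RF subset analyses. A reader could take a subset of about 50 children as well powered and treat a null result there as evidence of no effect.

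**Working it through.** **Inputs.** From section 9.1: r=.48 and .40, alpha .05, power 90%, n=42, 60 and 246, and r=.20. From section 9.2: two measures, three networks, Bonferroni within a family. Assumed here because the protocol does not say: two-sided tests, and family sizes m of 2 (two measures), 3 (three networks) and 6 (two measures in three networks).

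**Formulas** (Fisher z for a correlation, alpha = .05/m):
- required n = ((z_{1−alpha/2} + z_{.90}) / atanh r)² + 3
- power = Φ(atanh(r)·√(n−3) − z_{1−alpha/2})
- minimum detectable r = tanh((z_{1−alpha/2} + z_{.90}) / √(n−3))

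Constants: z_{.90} = 1.2816; atanh(.48) = .5230; atanh(.40) = .4236; atanh(.20) = .2027.

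**Step 1: reproduce the plan's figures (m=1, z = 1.960).**
- r=.48: (3.2415/.5230)² + 3 = 41.4, so 42. Stated: 42.
- r=.40: (3.2415/.4236)² + 3 = 61.5, so 62. Stated: 60. Power at n=60 is Φ(.4236·√57 − 1.960) = 89.2%.
- n=246: tanh(3.2415/√243) = .205. Stated: .20. Power at r=.20 is 88.5%. One-sided .05 would give .186, so two-sided .05 is the level that fits.

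The small gap at r=.40 depends on method: a noncentral-t calculation gives 38 and 58, and inflating the variance by 1.06 for Spearman correlations gives 44 and 66. The stated figures are sound for one test at two-sided .05.

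**Step 2: apply the plan's Bonferroni rule.**

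| m | alpha | z | power, n=42, r=.48 | power, n=60, r=.40 | n needed (r=.48 / .40) | detectable r, n=246 |
|---|---|---|---|---|---|---|
| 1 | .05 | 1.960 | 90.4% | 89.2% | 42 / 62 | .205 |
| 2 | .025 | 2.241 | 84.7% | 83.1% | 49 / 73 | .222 |
| 3 | .0167 | 2.394 | 80.8% | 78.9% | 53 / 79 | .232 |
| 6 | .0083 | 2.638 | 73.5% | 71.2% | 60 / 89 | .246 |

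Example, m=2 and n=42: .5230·√39 − 2.241 = 1.025, and Φ(1.025) = 84.7%.

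**Step 3: detectable r at the stated subset sizes, 90% power.**

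| m | n=42 | n=60 |
|---|---|---|
| 1 | .477 | .405 |
| 2 | .511 | .436 |
| 3 | .529 | .452 |
| 6 | .556 | .477 |

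**Step 4: dependence on the effect size (illustration only).** The documents give no PTB-RF effect. At unadjusted alpha .05, an assumed r=.30 gives power of 48.9% at n=42 and 64.7% at n=60; an assumed r=.20 gives 24.4% and 33.4%.

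**The case against.** The strongest reply is that section 9.1 contains no error. It claims 90% power at alpha .05 for two named effects, and that is true to within rounding. It calls the analysis indicative, says why a proxy was needed and names the proxy. The Bonferroni rule is conditional and no family is defined. The attention and language time courses are described as exploratory, with correction by permutation, so the confirmatory family may be small. WP3 draws on an existing cohort, so n=42 and n=60 did not set its size.

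Much of this stands, and it rules out several stronger readings.

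- *That the figures are miscalculated.* They reproduce.
- *That the plan relies on an age effect that cannot occur in 5-year-olds.* The protocol does not propose to test age from 3 to 5. It uses that effect as a yardstick for the size of individual differences.
- *That the loss is the six-test figure.* Six is one end of an assumed range. If every test were its own family, no correction would apply and the stated power would stand, though the protocol does not say so.
- *That PTB-RF subsets have 24% to 65% power.* Those values follow only from assuming r=.20 or .30.
- *That the full-sample figure fails with the age effect.* The n=246 statement does not use it; only the alpha point touches it.

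What the reply does not meet is the mismatch itself. Even the smallest family suggested by the plan, the two social-network measures that section 9.1 itself powers, takes power below 90%. Disclosing a proxy explains why it was chosen; it does not make it evidence about PTB-RF contrasts.

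**Conclusion.** The point holds as a mismatch between the power statement and the planned analysis. At two-sided alpha, 90% power is not kept at n=42 or n=60 for any Bonferroni family of two or more tests. For 2 to 6 tests it falls to between 84.7% and 73.5% (n=42) and between 83.1% and 71.2% (n=60), and the 90%-power detectable r at n=246 rises from .205 to between .222 and .246. These figures rest on the Fisher approximation and on assumed family sizes.

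The second part is narrower: n=42/60 does not show that PTB-RF subsets of that size are adequately powered, because the age effect over 3 to 5 years is a benchmark and not an estimate of a PTB-RF effect at 5 years. The documents do not show that such subsets are underpowered by any particular amount.

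This is worth correcting but is not a must-fix: the estimate is labelled indicative, the full-sample loss is modest and the cohort size does not depend on it.

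**What to change.** In section 9.1 (WP3):

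1. State which tests form a Bonferroni family and how many there are, consistently with section 9.2.
2. Restate the n=246 sensitivity at the adjusted two-sided alpha: about r=.22 for two tests to .25 for six.
3. Replace the n=42/60 sentence with the 90%-power minimum detectable r by subset size at that alpha: for n=42, about .51 (two tests) to .56 (six); for n=60, about .44 to .48.
4. Say that the age effect is only a benchmark for size, and label PTB-RF subset analyses of that size exploratory.

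The cost is wording and a less favourable stated sensitivity. No extra children are needed.
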